9.1.9 Tazemetostat Toxicities

Comprehensive Adverse Events and Potential Risks list (CAEPR) for Tazemetostat (NSC 791066)

The Comprehensive Adverse Events and Potential Risks list (CAEPR) provides a single list of reported and/or potential adverse events (AE) associated with an agent using a

uniform presentation of events by body system. In addition to the comprehensive list, a subset, the Specific Protocol Exceptions to Expedited Reporting (SPEER), appears in a separate column and is identified with bold and italicized text. This subset of AEs (SPEER) is a list of events that are protocol specific exceptions to expedited reporting to NCI (except as noted below). Refer to the 'CTEP, NCI Guidelines: Adverse Event Reporting Requirements'

http://ctep.cancer.gov/protocolDevelopment/electronic_applications/docs/aeguidelines.pdf for further clarification. Frequency is provided based on 815 patients. Below is the CAEPR for Tazemetostat.

NOTE: Report AEs on the SPEER **ONLY IF** they exceed the grade noted in parentheses next to the AE in the SPEER. If this CAEPR is part of a combination protocol using multiple investigational agents and has an AE listed on different SPEERs, use the lower of the grades to determine if expedited reporting is required.

Version 2.4, March 30, 2021¹

Adverse Events with Possible Relationship to Tazemetostat (CTCAE 5.0 Term) [n= 815]			Specific Protocol Exceptions to Expedited Reporting (SPEER)
Likely (>20%)	Less Likely (<=20%)	Rare but Serious (<3%)	
BLOOD AND LYMPHATIC SYSTEM DISORDERS			
	Anemia		
GASTROINTESTINAL DISORDERS			
	Constipation		
	Diarrhea		
	Nausea		Nausea (Gr 2)
	Vomiting		Vomiting (Gr 2)
GENERAL DISORDERS AND ADMINISTRATION SITE CONDITIONS			
	Fatigue		Fatigue (Gr 2)
INVESTIGATIONS			
	Neutrophil count decreased		
	Platelet count decreased		Platelet count decreased (Gr 2)
	Weight loss		
METABOLISM AND NUTRITION DISORDERS			
	Anorexia		
NEOPLASMS BENIGN, MALIGNANT AND UNSPECIFIED (INCL CYSTS AND POLYPS)			
		Leukemia secondary to oncology chemotherapy	
		Myelodysplastic syndrome	
		Treatment related secondary malignancy ²	
RESPIRATORY, THORACIC AND MEDIASTINAL DISORDERS			
		Cough	
		Dyspnea	
SKIN AND SUBCUTANEOUS TISSUE DISORDERS			
	Alopecia		
	Dry skin		
		Photosensitivity	

¹ This table will be updated as the toxicity profile of the agent is revised. Updates will be distributed to all Principal

Investigators at the time of revision. The current version can be obtained by contacting [contact]. Your name, the name of the investigator, the protocol and the agent should be included in the e-mail.

² Treatment related secondary malignancies includes Peripheral T-cell lymphoma (PTCL), T-cell lymphoblastic lymphoma (T-LBL), and B-cell acute lymphoblastic leukemia (B-ALL). It may be worth noting that the adult patient observed with B-ALL may be due to an underlying Diffuse large B-cell lymphoma (DLBCL).

Adverse events reported on tazemetostat trials, but for which there is insufficient evidence to suggest that there was a reasonable possibility that tazemetostat caused the adverse event:

BLOOD AND LYMPHATIC SYSTEM DISORDERS - Blood and lymphatic system disorders - Other (pancytopenia); Febrile neutropenia

CARDIAC DISORDERS - Chest pain - cardiac; Left ventricular systolic dysfunction

EAR AND LABYRINTH DISORDERS - Vertigo

ENDOCRINE DISORDERS - Hypothyroidism

EYE DISORDERS - Dry eye; Periorbital edema; Vision decreased; Watering eyes

GASTROINTESTINAL DISORDERS - Abdominal distension; Abdominal pain; Dry mouth; Dyspepsia; Dysphagia; Flatulence; Gastric perforation; Gastrointestinal disorders - Other (defecation urgency); Hemorrhoids; Mucositis oral; Rectal hemorrhage; Toothache

GENERAL DISORDERS AND ADMINISTRATION SITE CONDITIONS - Chills; Edema limbs; Fever; Flu like symptoms; General disorders and administration site conditions - Other (early satiety); General disorders and administration site conditions - Other (general physical health deterioration); Localized edema; Malaise; Non-cardiac chest pain

HEPATOBIILIARY DISORDERS - Gallbladder obstruction; Hepatobiliary disorders - Other (hepatocellular injury)

INFECTIONS AND INFESTATIONS - Conjunctivitis; Device related infection; Esophageal infection; Infections and infestations - Other (lower respiratory tract infection); Lung infection; Pharyngitis; Sepsis; Sinusitis; Skin infection; Soft tissue infection; Upper respiratory infection; Urinary tract infection

INJURY, POISONING AND PROCEDURAL COMPLICATIONS - Wound dehiscence

INVESTIGATIONS - Alanine aminotransferase increased; Aspartate aminotransferase increased; Blood bilirubin increased; CPK increased; Electrocardiogram QT corrected interval prolonged; Investigations - Other (c-reactive protein increased); Lymphocyte count decreased; Serum amylase increased; White blood cell decreased

METABOLISM AND NUTRITION DISORDERS - Dehydration; Hyperglycemia; Hyperkalemia; Hyperlipidemia; Hypertriglyceridemia; Hypokalemia; Hyponatremia; Hypophosphatemia; Metabolism and nutrition disorders - Other (diabetic metabolic decompensation); Metabolism and nutrition disorders - Other (polydipsia)

MUSCULOSKELETAL AND CONNECTIVE TISSUE DISORDERS - Arthralgia; Back pain; Muscle cramp; Myalgia; Neck pain; Pain in extremity

NEOPLASMS BENIGN, MALIGNANT AND UNSPECIFIED (INCL CYSTS AND POLYPS) - Tumor hemorrhage; Tumor pain

NERVOUS SYSTEM DISORDERS - Dizziness; Dysesthesia; Dysgeusia; Dysphasia; Headache; Hydrocephalus; Lethargy; Memory impairment; Nervous system disorders - Other (vocal cord paralysis); Paresthesia; Peripheral motor neuropathy; Peripheral sensory neuropathy; Radiculitis; Seizure

PSYCHIATRIC DISORDERS - Anxiety; Depression; Hallucinations; Insomnia; Psychiatric disorders - Other (mood swings)

RENAL AND URINARY DISORDERS - Proteinuria; Renal and urinary disorders - Other (polyuria); Urinary frequency

REPRODUCTIVE SYSTEM AND BREAST DISORDERS - Reproductive system and breast disorders - Other (vulvovaginal rash)

RESPIRATORY, THORACIC AND MEDIASTINAL DISORDERS - Bronchopulmonary hemorrhage; Epistaxis; Hypoxia; Nasal congestion; Oropharyngeal pain; Pleural effusion; Pulmonary edema; Respiratory failure; Respiratory, thoracic and mediastinal disorders - Other (tachypnea)

SKIN AND SUBCUTANEOUS TISSUE DISORDERS - Bullous dermatitis; Hair color changes; Hair texture abnormal; Hirsutism; Hyperhidrosis; Hypertrichosis; Nail ridging; Pruritus; Purpura; Rash acneiform; Rash maculopapular; Skin and subcutaneous tissue disorders - Other (psoriasis); Skin hyperpigmentation; Urticaria

VASCULAR DISORDERS - Hot flashes; Hypertension; Superior vena cava syndrome; Thromboembolic event; Vascular disorders - Other (peripheral venous disease)

Note: Tazemetostat in combination with other agents could cause an exacerbation of any adverse event currently known to be caused by the other agent, or the combination may result in events never previously associated with either agent.

Note: AESI: Based on preclinical findings in toxicology studies, FDA has requested the following Adverse Events of Special Interest (AESI) to be reported in an expedited manner: 1) T-cell lymphoma; and 2) abnormal bone growth. It should be noted that abnormal bone growth has not been observed in clinical trials of tazemetostat.

9.2 Agent Ordering and Agent Accountability

NCI-supplied agents may be requested by eligible participating Investigators (or their authorized designee) at each participating institution. The CTEP-assigned protocol number must be used for ordering all CTEP-supplied investigational agents. The eligible participating investigators at each participating institution must be registered with CTEP, DCTD through an annual submission of FDA Form 1572 (Statement of Investigator), NCI Biosketch, Agent Shipment Form, and Financial Disclosure Form (FDF). If there are several participating investigators at one institution, CTEP-supplied investigational agents for the study should be ordered under the name of one lead participating investigator at that institution.

Note: No starter supplies will be provided. Study agent must be ordered after enrollment and treatment assignment to APEC1621C with consideration for timing of processing and shipping to ensure receipt of drug supply prior to start of protocol therapy. If expedited shipment is required, sites should provide an express courier account through the Online Agent Order Processing (OAOP) application. Provide the patient ID number in the comment field when submitting an order request.

9.3 Clinical Drug Request and Investigator Brochure Availability

Submit agent requests through the PMB Online Agent Order Processing (OAOP) application. The current versions of the IBs for the agents will also be accessible to site investigators and research staff through the PMB Online Agent Order Processing (OAOP) application. Access to OAOP requires the establishment of a CTEP Identity and Access Management (IAM) account and the maintenance of an “active” account status, a “current” password, and active person registration status. For questions about drug orders, transfers, returns, or accountability call or email PMB anytime. Refer to the PMB’s website for specific policies and guidelines related to agent management. Questions about IB access may be directed to the PMB IB coordinator via email.

9.4 Agent Inventory Records

The investigator, or a responsible party designated by the investigator, must maintain a careful record of the receipt, dispensing and final disposition of all agents received from the PMB using the appropriate NCI Investigational Agent (Drug) Accountability Record (DARF) available on the CTEP forms page. Store and maintain separate NCI Investigational Agent Accountability Records for each agent, strength, formulation and ordering investigator on this protocol.

10.0 CRITERIA FOR REMOVAL FROM PROTOCOL THERAPY AND OFF STUDY CRITERIA

10.1 Criteria for Removal from Protocol Therapy

- a) Clinical (including physical examination or serum tumor markers) or radiographic evidence of progressive disease (See [Section 12](#)).
- b) Adverse Events requiring removal from protocol therapy (See [Section 6](#)).
- c) Refusal of protocol therapy by patient/parent/guardian
- d) Non-compliance that in the opinion of the investigator does not allow for ongoing participation.
- e) Completion of 26 cycles of therapy;
- f) Physician determines it is not in the patient's best interest.
- g) Repeated eligibility laboratory studies (CBC with differential, bilirubin, ALT (SGPT) or serum creatinine) are outside the parameters required for eligibility prior to the start of protocol therapy (See [Section 8.1](#)).
- h) Study is terminated by Sponsor.
- i) Pregnancy
- j) Patient did not receive protocol treatment after study enrollment.

Patients who are removed from protocol therapy during cycle 1 should continue to have the required observations in [Section 8.1](#) until the originally planned end of the cycle or until all adverse events have resolved per [Section 13.4.4](#), whichever happens LATER. The only exception is with documentation of the patient's withdrawal of consent from the APEC1621SC screening protocol. Patients who are removed from protocol therapy in subsequent cycles should have the necessary observations to ensure adequate clinical care.

10.2 Follow-Up Data Submission and APEC1621SC Off Study Criteria

Patients who are off subprotocol therapy will continue to be followed on the APEC1621SC screening protocol. Follow-up data submission will occur until one of the APEC1621SC Off Study Criteria is met (See Section 10 of APEC1621SC for details). Ongoing adverse events, or adverse events that emerge after the patient is removed from protocol therapy, but within 30 days of the last dose of investigational agent, must be followed and reported via RAVE and CTEP-AERS (if applicable). Follow-up data will be required until off study criteria are met unless consent is withdrawn or the patient dies or is lost to follow-up.

11.0 STATISTICAL AND ETHICAL CONSIDERATIONS

11.1 Sample Size

APEC1621C will require a minimum of 20 evaluable patients and a maximum of 49 patients, allowing for 15% inevaluability. Assuming an enrollment rate of 4-9 biomarker positive patients per year, the primary cohort of this subprotocol is expected to be completed within 2.7-6 years.

11.2 Dosing Considerations

Please see [Section 5.1](#) for a specific discussion of the dosing of tazemetostat to be used in this study, based on site of disease.

11.3 Study Design

The primary cohort will employ a single stage A'Hern designs of N=20. Tazemetostat will be deemed worthy of further study in the relevant subset of patients (i.e. biomarker positive in any histology, biomarker positive in a particular histology, etc) if the decision rule is met. Operating characteristics are shown below.

Cohort	N	Decision Rule	Alpha	Power
Primary biomarker positive	20	≥ 3 responses	10%	90%

Per amendment 3B, Tazemetostat will be administered at a dose of 520 mg/m²/dose BID for patients without any CNS involvement; or 1200 mg/m²/dose BID for patients with CNS involvement. The response will be examined in the combined primary cohort consisting of patients with or without CNS involvement. Patients who enrolled pre-amendment #3B treated with at 1200 mg/m²/dose BID and meet evaluation criteria will also be counted in the evaluation.

Histology-specific biomarker positive expansion cohorts will, by definition, be deemed worthy of further study, since they will have at least 3 responses. The table below shows 90% confidence intervals (Wilson method) for a range of observable response rates.

Cohort Size	Observed Response Rate	90% Confidence Interval
10	30%	13% - 56%
10	40%	19% - 65%
10	50%	27% - 73%

11.3.1 Primary Cohort:

APEC1621C will evaluate a primary cohort of 20 mutation-matched ("biomarker positive") evaluable patients of any histology for the primary study aim of determining the objective response rate (CR/PR according to the response criteria in [Section 12.3](#)) to tazemetostat. Using an A'Hern design⁸ with alpha=10%, a sample of N=20 will provide 90% power to detect an improvement in response rate from 5%, if the treatment is ineffective, to 25% if the targeted therapy is sufficiently effective to warrant further study. If there are at least 3 responses out of 20 in the primary cohort, the biomarker/therapy match will be deemed a success.

If at any time, there is one occurrence of secondary T-cell lymphomas in patients exposed to tazemetostat, we will suspend the accrual and consider dose, schedule

or duration of treatment modification. The COG DSMC will be notified and CTEP consulted regarding the next steps to take with respect to the protocol.

11.3.2 **Histology-Specific Biomarker Positive Expansion Cohorts:**

If ≥ 3 patients in the primary cohort with the same histology show signs of objective response (CR/PR according to the response criteria in [Section 12.3](#)), a histology-specific biomarker positive expansion cohort will open after the primary cohort is completed to up to 7 evaluable patients for a total sample size of 10 evaluable biomarker positive patients with that histology. This will allow us to estimate more precisely the activity in biomarker positive patients of that histology. See [Appendix VI](#) for a list of target tumor histologies/types.

We will open up to 3 such expansion cohorts for biomarker positive patients (i.e., if 3 histologies have ≥ 3 responses, we will open a total of 3 expansion cohorts as described above). Note that this can only happen if the response rate in the primary cohort is at least 45% (9/20) and there cannot be more than 21 additional evaluable patients in total for these expansion cohorts.

11.4 **Methods of Analysis**

Response criteria are described in [Section 12](#). A responder is defined as a patient who achieves a best response of PR or CR on the study. Response rates will be calculated as the percent of evaluable patients who are responders, and confidence intervals will be constructed using the Wilson score interval method.⁹ Decision making for A'Hern design cohorts will follow rules described above.

Toxicity tables will be constructed to summarize the observed incidence by type of toxicity and grade. A patient will be counted only once for a given toxicity for the worst grade of that toxicity reported for that patient. Toxicity information recorded will include the type, severity, time of onset, time of resolution, and the probable association with the study regimen.

11.5 **Evaluability for Response**

Any eligible patient who is enrolled and receives at least one dose of protocol therapy will be considered evaluable for response. Any patient who receives non-protocol anti-cancer therapy during the response evaluation period will be considered a non-responder for the purposes of the statistical rule, unless they show an objective response prior to receiving the non-protocol anti-cancer therapy (in which case they will be considered a responder). Patients who demonstrate a complete or partial response confirmed by central review will be considered to have experienced a response. When opening expansion cohorts, the evaluation period for determination of best response will be 6 treatment cycles. All other patients will be considered non-responders. Patients who are not evaluable for response evaluation may be replaced for the purposes of the statistical rule. All patients considered to have a response (CR or PR) must have imaging studies reviewed centrally at the COG. Centers will be notified by the COG about requests for scans of patients with stable disease. Preliminary assessment of activity using institutionally provided tumor measurements will be entered into CDUS quarterly. The central review by COG will be provided as the final reviewed assessment of response when such becomes available.

11.6 **Evaluability for Toxicity**

All eligible patients who receive at least one dose of protocol therapy will be considered in the evaluation of toxicity.

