1.0 GOALS AND OBJECTIVES (SCIENTIFIC AIMS)

1.1 Primary Aims

- 1.1.1 To determine the objective response rate (ORR; complete response + partial response) in pediatric patients treated with tazemetostat with advanced solid tumors (including CNS tumors), non-Hodgkin lymphoma or histiocytic disorders that harbor gain of function mutations in EZH2, or loss of function mutations in the SWI/SNF complex subunits SMARCB1 or SMARCA4 at a dose of 520 mg/m²/dose twice daily for patients without any CNS involvement or 1200 mg/m²/dose orally twice daily for patients with CNS involvement.

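### Toxicity tables leave out treated ineligible patients and do not mention dose; the pooled response rate counts pre-#3B patients whatever their CNS status, and no response rate by regimen is planned

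*Combined protocol and SAP*

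**What the plan says.** **Toxicity set.** Section 11.6: "All eligible patients who receive at least one dose of protocol therapy will be considered in the evaluation of toxicity".

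**Toxicity tables.** Section 11.4: "Toxicity tables will be constructed to summarize the observed incidence by type of toxicity and grade". Each patient counts once per toxicity, at the worst grade. Dose is not mentioned.

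**Response set.** Section 11.3: "The response will be examined in the combined primary cohort consisting of patients with or without CNS involvement". It adds: "Patients who enrolled pre-amendment #3B treated with at 1200 mg/m²/dose BID and meet evaluation criteria will also be counted in the evaluation". No condition on CNS involvement is attached to that second sentence.

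**Aim.** Aim 1.1.1 defines the objective response rate (ORR) "at a dose of 520 mg/m²/dose twice daily for patients without any CNS involvement", and at 1200 mg/m² for patients with CNS involvement. Section 5.1 gave every pre-#3B patient 1200 mg/m².

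**Decision rule.** Section 11.3.1 uses an A'Hern design: "with alpha=10%, a sample of N=20 will provide 90% power". The null response rate is 5% and the target is 25%. Three or more responses among 20 is a success for the biomarker/therapy match as a whole. Sections 11.3 to 11.8 plan no response rate by dose or by CNS involvement.

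**The concern.** Section 2.7 gives the reason for the lower dose: limiting exposure and possible secondary malignancy. Section 2.4.2 reports that mean exposure in children at 1200 mg/m² exceeded that of adults at 1600 mg twice daily. The two starting doses differ by a factor of 1200/520 = 2.31. A toxicity table that does not separate them describes neither dose, and tolerability is a secondary aim (1.2.2).

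Section 4.0 says that the eligibility criteria are read literally, cannot be waived, and are verified at audit. A dosed patient can therefore be ruled ineligible afterwards. That child was exposed to the drug, and removing them from an incidence table has no safety rationale.

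For response, a pre-#3B patient without CNS involvement was treated at a dose that aim 1.1.1 does not assign to such patients, yet counts towards the 3 responses. A reader who sees a pass will also want to know whether it says anything about 520 mg/m². Section 2.7 supports activity at that dose with one patient who had prolonged benefit.

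**Working it through.** **1. The stated design reproduces.** Inputs from Section 11.3: N = 20, success at 3 or more responses, null rate 5%, target rate 25%. With X ~ Bin(20, p):
- P(X ≥ 3 | p = 0.05) = 0.0755
- P(X ≥ 3 | p = 0.25) = 0.9087

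N = 20 is the smallest sample with alpha at most 10% and power at least 90%. The stated 10% is a ceiling; the attained alpha is 7.55%. Both figures assume one common response rate.

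**2. What a pass means if the regimens differ.** The documents do not give the split by regimen, so it is an assumption here. Let A ~ Bin(n₁, 0.25) and B ~ Bin(20 − n₁, 0.05). P(A + B ≥ 3) is:

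| Patients at 25% / at 5% | P(pass) |
|---|---|
| 3 / 17 | 20.6% |
| 5 / 15 | 32.1% |
| 10 / 10 | 60.4% |
| 15 / 5 | 80.1% |
| 17 / 3 | 85.3% |

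**3. Is the 60.4% caused by pooling?** The average rate at 10/10 is (10 × 0.25 + 10 × 0.05)/20 = 15%. A homogeneous cohort at 15% has P(Bin(20, 0.15) ≥ 3) = 59.5%. So the 60% reflects an average rate of 15%, not a distortion from mixing.

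**4. What pooling does hide is the source of the responses.** In the 10/10 case:
- P(A ≥ 3) = 0.4744
- P(B = 0) = 0.95¹⁰ = 0.5987
- P(A ≥ 3 and B = 0) = 0.4744 × 0.5987 = 0.2840
- Share of passes with no response in the 5% stratum = 0.2840/0.6042 = 47%

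**5. What results by regimen could show.** With 10 patients in a regimen, the 90% Wilson interval is 13–56% for 3/10 (the plan's own figure) and 0–21% for 0/10. Applying the rule of 3 or more within 10 patients would have alpha 1.2% and power 47.4%. A separate test per regimen at the stated alpha and power would need 20 evaluable patients each, 40 in total. Results by regimen can therefore only be descriptive.

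**6. Pre-#3B patients without CNS involvement.** Their number is not given. If there were one, and that patient responded, a result of 3/20 = 15% would become 2/19 = 10.5% without them. If there are none, the two figures coincide.

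**7. Toxicity.** The number of treated ineligible patients is not given either, so the effect on the tables cannot be sized. For precision by dose: with no events seen, the one-sided 95% upper bound 1 − 0.05^(1/n) is 13.9% at n = 20 and 25.9% at n = 10.

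**The case against.** The strongest reply is that pooling is deliberate and disclosed. Aim 1.1.1 asks for one response rate under one dosing policy, and the rule tests that policy. The cohort already combines any histology and three genes, and a pass means only that the match deserves further study. This stands. A reader might infer that no regimen's activity or safety is shown by the trial; the documents do not support that. What is missing is activity and safety by dose level.

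A reader might also take the 60% as a false-positive rate created by pooling. It is not, as step 3 shows, and the split and rates behind it are assumed.

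On toxicity, Section 11.4 is silent on dose. It neither orders pooling nor rules out tables by dose, and dose is recorded at enrollment (Section 3.8) and on the delivery map (Appendix V). The T-cell lymphoma risk behind #3B is also handled outside the tables: Section 6.1 separates cases above 520 mg/m² from those at or below it, and Section 11.3.1 suspends accrual after one case. These points stand, but they leave the content of the tables unspecified.

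Nor does a treated ineligible child vanish from safety oversight. Expedited reporting (Section 13.2), routine reporting (Section 13.5.1) and CDUS reporting (Section 14.2) carry no eligibility condition. That limits the gap to the incidence tables; it does not close it.

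Finally, after #3B dose is fixed by CNS involvement, so strata by regimen mix dose with disease site. This is correct, and it is why such results should be labelled descriptive.

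**Conclusion.** The point holds as a set of gaps in analysis sets and reporting. It is not a flaw in the sample size or the decision rule.

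- **Firm, from the text:** Section 11.6 leaves treated ineligible patients out of the toxicity evaluation. Section 11.3 counts pre-#3B patients whatever their CNS status. No response rate by regimen is planned.
- **Inferred from silence:** that toxicity would be tabulated without regard to dose.
- **Unknown size:** the numbers of treated ineligible patients and of pre-#3B patients without CNS involvement. Either may be zero. Pre-#3B patients with CNS involvement fit the aim and raise no issue.
- **Illustration only:** the 60% pass probability and the 47% of passes with no response in the weaker stratum rest on an assumed 10/10 split with rates of 25% and 5%. Over splits from 3/17 to 17/3 the pass probability runs from 20.6% to 85.3%.

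The sponsor should make the changes, preferably before results are seen.

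**What to change.** - **Section 11.6:** define the toxicity set as every patient who received at least one dose, whatever their eligibility.
- **Section 11.4, toxicity:** tabulate by assigned starting dose as well as by type and grade.
- **Section 11.3 or 11.4, response:** keep N = 20 and the rule of 3 or more. Add the primary ORR without pre-#3B patients who had no CNS involvement, and state how many there are.
- **Section 11.4, by regimen:** report ORR with 90% Wilson intervals for non-CNS at 520 mg/m², CNS at 1200 mg/m², and pre-#3B non-CNS at 1200 mg/m² if any. Label these descriptive, note that dose is confounded with CNS involvement, and attach no decision rule.

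The cost is a few extra tables and wide intervals in small strata. Accrual, dosing and the decision rule do not change.

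### Expansion-cohort response rates count the responders that opened the cohort, so the 10-patient ORR is biased upward and its ordinary 90% Wilson interval can fall well short of 90% coverage

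*Combined protocol and SAP*

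**What the plan says.** The trigger is in section 11.3.2: "If ≥ 3 patients in the primary cohort with the same histology show signs of objective response", an expansion cohort for that histology opens once the primary cohort is complete. The expansion adds "up to 7 evaluable patients for a total sample size of 10 evaluable biomarker positive patients with that histology". The 10 therefore include the primary-cohort patients of that histology, among them the responders who caused the cohort to open.

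Section 11.3 confirms the pooling: "Histology-specific biomarker positive expansion cohorts will, by definition, be deemed worthy of further study, since they will have at least 3 responses". Its table gives 90% Wilson intervals for a cohort of 10 and starts at an observed rate of 30%.

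Section 11.3.2 gives the purpose as estimation: "This will allow us to estimate more precisely the activity in biomarker positive patients of that histology". On method, section 11.4 says "Response rates will be calculated as the percent of evaluable patients who are responders" and "confidence intervals will be constructed using the Wilson score interval method". Section 11 contains no selection adjustment, no separate analysis of the newly enrolled patients, and no caveat on the pooled figure.

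**The concern.** A Wilson interval treats the count as an unselected binomial. Here the count is reported only for histologies that have already produced at least 3 responses, and those responses stay in the numerator. The result cannot be 0, 1 or 2 out of 10. If none of 7 new patients respond, the plan still reports 3/10 with an interval of 13% to 56%.

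What is at stake is the histology-specific ORR that readers would take from the trial. The expansion exists to sharpen that estimate, yet the selected early patients pull it upward. Appendix VI lists 15 named histologies plus an open category, and up to 3 cohorts may open, so the reported cohorts are those with the best early results.

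**Working it through.** **Inputs from the plan.** Trigger of at least 3 responders of one histology in the primary cohort; total of 10 with at most 7 new (11.3.2). Raw proportion and Wilson interval (11.4). 90% level, and response rates of 5% (ineffective) and 25% (target) (11.3, 11.3.1).

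**Assumption.** m, the number of primary-cohort patients with the histology, is not given. I take m = 3 to 10; above 10 there is no room for an expansion.

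**Step 1: the plan's own table.** Wilson limits are [p̂ + z²/2n ± z√(p̂(1−p̂)/n + z²/4n²)] / (1 + z²/n), with z = 1.645 and n = 10.
- 3/10: 12.7% to 55.8%
- 4/10: 19.4% to 64.8%
- 5/10: 26.9% to 73.1%

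These match the printed 13%-56%, 19%-65% and 27%-73%. The arithmetic is right; the question is the sample to which it is applied.

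**Step 2: the model.** X1 ~ Bin(m, p) for primary patients, observed only if X1 ≥ 3. Y ~ Bin(10−m, p) for new patients. The reported rate is (X1 + Y)/10. Its conditional mean is [E(X1 | X1 ≥ 3) + (10−m)p]/10. This exceeds p for every p below 100%, because E(X1 | X1 ≥ 3) > mp.

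**Step 3: worked case, m = 5 and p = 25%.**
- P(X1 = 3, 4, 5) = 0.0879, 0.0146, 0.0010, so P(open) = 0.1035.
- Given opening, these become 0.849, 0.142, 0.009, and E(X1) = 3.16.
- Mean pooled ORR = (3.16 + 5 × 0.25)/10 = 44.1%.
- The interval contains 25% only for totals of 3 or 4, since the lower limit at 5/10 is already 26.9%.
- With Y ~ Bin(5, 0.25), P(Y = 0) = 0.237 and P(Y = 1) = 0.396. Coverage = 0.849 × (0.237 + 0.396) + 0.142 × 0.237 = 57.1%.

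Without selection, Wilson coverage at n = 10 and p = 25% is 86.6%, so most of the shortfall comes from the trigger.

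**Step 4: the range, by exact enumeration.** Each cell runs from m = 3 to m = 10.

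| True ORR | Chance of opening, per histology | Mean pooled ORR | Conditional coverage |
|---|---|---|---|
| 5% | 0.01% to 1.2% | 33.5% to 31.0% | 0% |
| 10% | 0.1% to 7.0% | 37.0% to 32.1% | 0% |
| 25% | 1.6% to 47.4% | 47.5% to 36.9% | 44.5% to 83.5% |
| 40% | 6.4% to 83.3% | 58.0% to 44.6% | 71.0% to 93.4% |
| 50% | 12.5% to 94.5% | 65.0% to 51.9% | 77.3% to 94.2% |

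Coverage is 0% for any true rate below 12.7%, because that is the smallest lower limit that can be reported. It is 90.6% to 93.4% at true 40% with m = 7 to 10, and 91.7% to 94.2% at true 50% with m = 6 to 10.

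**Step 5: what an adjusted estimate does.** Maximise p^k(1−p)^(10−k) / P(X1 ≥ 3 | m, p). With m = 5, 4/10 becomes about 18%, 5/10 about 35% and 6/10 about 51%. A result of 3/10 goes to the lower boundary, since all of its responses were needed to open the cohort.

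**The case against.** The best defence has four parts.

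- **No confirmatory claim rests on it.** The expansion cohorts have no null rate, alpha or power, and a histology-specific ORR is not a separately listed aim in section 1. The primary rule is untouched. This stands, and it limits the severity.
- **The worst cases are rare.** At a true rate of 10% and m = 5 a given histology opens with probability 0.9%; at 5% the chance is at most 1.2% for m up to 10. This stands for low rates. At the 25% target, opening has probability 10% with m = 5 and 32% with m = 8, and conditional coverage is still 57% and 76%. The interval appears only when a cohort opens, so conditional performance is what its reader needs.
- **The selection is visible.** The trigger and the floor of 3 responses are both stated. This stands as disclosure, but it does not correct the estimate or the interval.
- **Pooling keeps scarce paediatric data.** This stands, and it argues for a conditional analysis of all 10 patients alongside the new-patient result.

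A reader might infer that the 90% interval never reaches its nominal level. The enumeration does not support that: with higher true rates and larger m it does. Wilson coverage at n = 10 also fluctuates around 90% without any selection.

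A reader might also infer that the statement about further study is a false test and should be decided by the new patients. Three responders in one histology already satisfy the rule of at least 3 in 20, so the statement claims no new test. Moving it to the new patients would create a decision rule for which the plan gives no threshold.

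**Conclusion.** The concern holds in this form: as written, the expansion ORR is biased upward for every true rate below 100%, and the ordinary Wilson interval undercovers over a wide part of the plausible range. At the protocol's 25% target the mean reported ORR is 47.5% to 36.9% and coverage 44% to 84%.

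The coverage figures depend on the assumed m of 3 to 10 and on independent binomial responses with a common rate in primary and new patients. They are conditional on the cohort opening. The existence of the upward bias does not depend on m.

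The documents do not support reading this as a flaw in the trial's main decision. It is a matter of estimation and reporting in cohorts that may never open. It should be fixed, but it is not a reason to hold the trial.

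**What to change.** In sections 11.3.2 and 11.4, specify two results for each expansion cohort:

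1. The ORR and 90% interval in the newly enrolled patients alone, using their actual number (10 − m, at most 7).
2. The pooled 10-patient ORR, labelled as including the patients who triggered the expansion, with an estimate and interval conditional on at least 3 primary-cohort responses in place of the ordinary Wilson interval.

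Where m is about 8 to 10 there are two, one or no new patients, so rely on the second result. Small numbers limit the first result too: for 5 to 7 new patients and true rates of 5% to 40%, its Wilson coverage runs from about 80% to 98%.

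Keep the n = 10 table only with a note that its intervals ignore the selection. Add new-patient intervals for each possible size; a table for 7 alone would fit only m = 3. With no responses the Wilson upper limit is z²/(n + z²), with z² = 2.706: 28% for n = 7 (2.706/9.706) and 35% for n = 5 (2.706/7.706).

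State that the finding of being worth further study for a histology reflects the primary-cohort trigger and is not confirmed by the expansion data.

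The cost is wording and a small table. Intervals will be wider and the headline ORR less favourable. No extra patients are needed.
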